Adult subjects will complete two questionnaires for quality of life: NNITS PRO EuroQOL-5 and NNITS PRO IBSQOL [\[30\]](#). There were no pediatric subjects enrolled in the study. The IBSQOL contains 34 items, each with a five-point response scale. The score for each subject/visit will be:

$$Score_{IBSQOL} = \frac{\text{The sum of the items} - \text{lowest possible score}}{\text{possible raw score range}} \times 100$$

If items are missing, confirm that at least 17 (50%) have been answered before calculating the score. If less than 17 questions have been answered, the score will be left as missing.

The scoring guide for the EuroQOL-5 questionnaire [31] states that a single index value is not currently possible. Instead, the levels will be dichotomized into ‘no problems’ (i.e. level 1) and ‘problems’ (i.e. levels 2 and 3).

Patient-Reported Physical Function:

Adult subjects will complete the NNITS PRO PROMIS [32] Physical Function questionnaire. The raw score will be the sum of the items from the questionnaire. The score for each subject/visit will then use the following table to convert the raw score into a t-score:

Physical Function 8b Short Form Conversion Table		
Raw Score	T-score	SE*
8	20.9	3.5
9	24.4	2.5
10	26.4	2.2
11	27.9	2.0
12	29.1	1.9
13	30.1	1.8
14	31.1	1.7
15	31.9	1.7
16	32.7	1.6
17	33.4	1.6
18	34.1	1.6
19	34.8	1.6
20	35.5	1.6
21	36.2	1.5
22	36.8	1.5
23	37.5	1.5
24	38.1	1.5
25	38.8	1.5
26	39.4	1.5
27	40.1	1.6
28	40.8	1.6
29	41.5	1.6
30	42.2	1.6
31	43.0	1.6
32	43.7	1.6
33	44.6	1.7
34	45.5	1.7
35	46.4	1.8
36	47.5	1.9
37	48.8	2.1
38	50.4	2.5
39	52.5	2.9
40	59.7	5.9

* SE = Standard error

Adult version

If items are missing, confirm that at least 4 (50%) have been answered before calculating the score. If less than 4 questions have been answered, the score will be left as missing. If less than 4 items are missing, the pro-rated raw score will be:

$$Raw\ score = \frac{Raw\ sum \times 8}{Number\ of\ items\ that\ were\ actually\ answered}$$

If the result is a fraction, round up to the nearest whole number.

Patient-Reported Emotional Distress:

Adult subjects will complete the NNITS PROMIS Emotional Questionnaire. Patient-reported emotional distress will be reported in three separate categories: depression, anxiety, and fatigue.

The raw score for depression will be the sum of questions #1-4. The depression score for each subject/visit will then use the following table to convert the raw score into a t-score:

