Depression 4a Short Form Conversion Table		
Raw Score	T-score	SE*
4	41.0	6.2
5	49.0	3.2
6	51.8	2.7
7	53.9	2.4
8	55.7	2.3
9	57.3	2.3
10	58.9	2.3
11	60.5	2.3
12	62.2	2.3
13	63.9	2.3
14	65.7	2.3
15	67.5	2.3
16	69.4	2.3
17	71.2	2.4
18	73.3	2.4
19	75.7	2.6
20	79.4	3.6

*SE = Standard Error

All questions must be answered to receive a depression score.

The raw score for anxiety will be the sum of questions #5-8. The anxiety score for each subject/visit will then use the following table to convert the raw score into a t-score:

Anxiety 4a Short Form Conversion Table		
Raw Score	T-score	SE*
4	40.3	6.1
5	48.0	3.6
6	51.2	3.1
7	53.7	2.8
8	55.8	2.7
9	57.7	2.6
10	59.5	2.6
11	61.4	2.6
12	63.4	2.6
13	65.3	2.7
14	67.3	2.7
15	69.3	2.7
16	71.2	2.7
17	73.3	2.7
18	75.4	2.7
19	77.9	2.9
20	81.6	3.7

*SE = Standard Error

All questions must be answered to receive an anxiety score.

The raw score for fatigue will be the sum of questions #9-12. The fatigue score for each subject/visit will then use the following table to convert the raw score into a t-score:

Fatigue 4a Short Form Conversion Table		
Raw Score	T-score	SE*
4	33.7	4.9
5	39.7	3.1
6	43.1	2.7
7	46.0	2.6
8	48.6	2.5
9	51.0	2.5
10	53.1	2.4
11	55.1	2.4
12	57.0	2.3
13	58.8	2.3
14	60.7	2.3
15	62.7	2.4
16	64.6	2.4
17	66.7	2.4
18	69.0	2.5
19	71.6	2.7
20	75.8	3.9

*SE = Standard Error

All questions must be answered to receive a fatigue score.

Patient-Reported Gastrointestinal Symptoms:

Adult subjects will complete the NNITS PROMIS GI Questionnaire. For question 17, each belly pain area marked “yes” will indicate 1 point (e.g. if a subject answers “yes” for belly pain area 1, belly pain area 6, and belly pain area 8, their score for question 17 would be 3). The GI Questionnaire contains questions from four domains: diarrhea (questions 1 – 3 and 8 – 10), nausea (questions 4 – 7), fecal incontinence (questions 11 – 14), and belly pain (questions 15 – 20) and therefore cannot be summarized into a single score. Instead each domain will be reported separately. The raw scores for each domain will be the sum of the items from the questionnaire that are in the domain. The score for each subject/visit will then use the following tables to convert the raw scores into t-scores:

Diarrhea:

Raw score	T-score
0	38.3
1	43.3
2	45.9
3	48.2
4	50.1
5	51.9
6	53.3
7	54.5
8	55.6
9	56.7
10	57.8
11	58.8
12	59.8
13	60.7
14	61.6
15	62.5
16	63.5
17	64.4
18	65.5
19	66.6
20	67.9
21	69.2
22	70.8
23	72.3
24	75.2

Nausea:

Raw score	T-score
0	40.3
1	45.0

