2	49.3
3	52.9
4	55.9
5	58.7
6	60.9
7	62.8
8	64.6
9	66.4
10	68.1
11	69.8
12	71.6
13	73.5
14	75.6
15	78.0
16	80.4

Fecal Incontinence:

Raw score	T-score
0	42.0
1	49.1
2	54.4
3	58.6
4	62.1
5	64.4
6	66.0
7	67.7
8	69.5
9	71.4
10	73.5
11	75.8
12	78.4
13	80.8
14	80.8
15	80.8
16	80.8

Belly Pain:

Raw score	T-score
0	31.7
1	37.2
2	40.6
3	43.5
4	46.2
5	48.6
6	50.7
7	52.6
8	54.3
9	55.9
10	57.5
11	59.1
12	60.5
13	61.9
14	63.2
15	64.5
16	65.8
17	67.0
18	68.3
19	69.5
20	70.8
21	72.1
22	73.5
23	74.9
24	76.1
25	76.9
26	77.9
27	78.6
28	78.6
29	82.1

If items are missing, confirm that at least 50% have been answered before calculating the score. If less than 50% of the questions have been answered, the score will be left as missing. If less than 50% of the items are missing, the pro-rated raw score will be:

$$\text{Raw score} = \frac{\text{Raw sum} \times \text{Total number of questions in domain}}{\text{Number of items that were actually answered}}$$

If the result is a fraction, round up to the nearest whole number. Note that only three of the four nausea questions from the GI questionnaire were included, therefore in order to meet the 50% criteria at least 2 of the 3 questions must be answered.

Positive and Negative Affect Scale (PANAS):

Adult subjects will complete the NNITS PROMIS PANAS Questionnaire. Patient-reported positive and negative affect scores will be reported in two separate categories: positive affect score and negative affect score.

The score for positive affect will be the sum of questions #1, 3, 5, 9, 10, 12, 14, 16, 17, and 19. The score for negative affect will be the sum of questions #2, 4, 6, 7, 8, 11, 13, 15, 18, and 20.

Reduction in Amount of Antimotility Agents:

The amount of antimotility agents for a given day will be defined as the response to the “# of antidiarrheals today” question in the Phase 1 (Treatment Phase) Daily Symptom Diary. Missing responses will be left as missing. 50% reduction in the amount of antimotility agents will be defined as the first study day in which the subject’s response was less than or equal to 50% of their response given on Day 1.

Number of Days of Diarrhea:

The number of days of diarrhea will be based on the Daily Diary Diarrhea Questions (see above). For a day to count towards the number of days of diarrhea, one of the following must occur: a quantitative diarrhea question must be greater than 0 or a qualitative question must be marked “yes”. Missing responses will be left as missing.

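### SAP 3.3 scores IBSQOL from as few as 17 of 34 items with no stated prorating, and its nausea rule is not right for every permitted form whether the domain counts as three or four questions

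*SAP*

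**What the plan says.** All scoring rules are in SAP section 3.3, under the detailed patient-reported measures.

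- **IBSQOL.** "The IBSQOL contains 34 items, each with a five-point response scale". The score is the item total minus the lowest possible score, divided by the possible range, times 100. For incomplete forms the SAP says "If items are missing, confirm that at least 17 (50%) have been answered before calculating the score" and "If less than 17 questions have been answered, the score will be left as missing". Nothing covers how to score 17 to 33 answers. The item coding is not given, nor whether the lowest score and range belong to all 34 items or only to those answered.
- **Physical Function.** Eight items with the same half-answered threshold, but here a scaling formula follows: "If less than 4 items are missing, the pro-rated raw score will be" the sum times 8 over the number answered.
- **GI domains.** The same threshold applies. When fewer than half the items are missing, the sum is multiplied by the number of questions in the domain over the number answered, and rounded up. Nausea is defined as questions 4 to 7. Its table runs from raw 0 (T 40.3) to raw 16 (T 80.4). A closing note says that "only three of the four nausea questions from the GI questionnaire were included" and asks for at least two of those three.

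SAP 6.5 limits imputation to diary data for the primary endpoint. SAP 8.3 analyses change in these scores by ANCOVA with the baseline score as covariate (Table 33), with a p-value at Day 180.

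**The concern.** If an unanswered IBSQOL item adds nothing to the sum while the limits stay those of the full form, the score drops with each skipped item whatever the respondent's condition. Change from baseline then partly measures how many items were skipped at each visit, and the error enters both the covariate and the outcome.

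For nausea, a sum from three items is converted with a table built for four. Whether it is first scaled up depends on whether the domain is taken to have three or four questions, and the text supports either. Two programmers could produce different nausea rows from the same data, and neither reading scores every permitted form correctly.

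**Working it through.** **Thresholds.** 0.5 × 34 = 17 and 0.5 × 8 = 4, as the SAP states. For nausea, 0.5 × 4 = 2, and 0.5 × 3 = 1.5 rounds up to 2. The two-of-three requirement therefore fits either domain size and does not settle which is meant.

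**IBSQOL.** Assumption: the lowest score and range refer to all 34 items. Coded 1–5, the lowest score is 34 and the range is 170 − 34 = 136. Coded 0–4, the lowest is 0 and the range is 136. Take a respondent who picks the middle category throughout, so the true score is 50:

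| Answered | Coded 1–5 | Coded 0–4 |
|---|---|---|
| 34 | (102 − 34)/136 = 50.0 | 68/136 = 50.0 |
| 33 | (99 − 34)/136 = 47.8 | 66/136 = 48.5 |
| 30 | (90 − 34)/136 = 41.2 | 60/136 = 44.1 |
| 17 | (51 − 34)/136 = 12.5 | 34/136 = 25.0 |

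At the extremes with 17 answered:
- All top category: (85 − 34)/136 = 37.5 coded 1–5, or 68/136 = 50.0 coded 0–4, instead of 100.
- All bottom category: (17 − 34)/136 = −12.5 coded 1–5, or 0 coded 0–4, instead of 0.

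Multiplying the sum by 34/answered first returns 0, 50 and 100 for these three patterns at any count from 17 to 34.

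**Nausea.** A table of 0–16 corresponds to four items scored 0–4. The reference is sum × 4/answered, rounded up, then looked up in the SAP table.

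- *Domain counted as three.* A complete form has nothing missing, so the sum is read directly. Sum 3 gives 52.9 against 55.9 (raw 4), 3.0 low. Sum 6 gives 60.9 against 64.6 (raw 8), 3.7 low. Sum 12 gives 71.6 against 80.4 (raw 16), 8.8 low. Over sums 1 to 12 the shortfall runs from 3.0 to 8.8. With two answered, sum 4 becomes 4 × 3/2 = 6, T 60.9, against 4 × 4/2 = 8, T 64.6.
- *Domain counted as four.* A complete three-item form is 25% missing, so it is scaled by 4/3 and matches the reference. A two-answer form is exactly 50% missing. It may be scored, but it is outside the prorating trigger, so sum 4 is read as 55.9 against 64.6, 8.7 low.

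**The same boundary elsewhere.** Physical Function allows a score from 4 of 8 answers, but prorates only with fewer than four missing. Four answers of 3 sum to 12, T 29.1. Scaled, 12 × 8/4 = 24, T 38.1, a difference of 9.0. The other GI domains have the same gap at exactly half answered.

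**The case against.** On IBSQOL, the SAP never says that the lowest score and range stay at their 34-item values. Computed on the answered items, the formula would prorate by itself. The SAP also cites the instrument's information sheet (reference 30), which may cover missing items. Study staff administer the questionnaires, so skipped items may be few, and the documents give no missingness rate. These points stand as limits on the size of the effect. They do not supply the missing rule: the SAP states prorating for the neighbouring scales and omits it here, and SAP 6.5 gives a programmer no licence to add it.

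On nausea, a reader might infer that every non-zero T-score is too low as the plan is written, and so that any nausea benefit would be understated. The documents do not support that. With the domain defined as questions 4 to 7, the SAP's own GI rule scales a complete form by 4/3, which is correct. What remains is an ambiguity, plus an error at two answers under that more favourable reading.

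A reader might also infer that IBSQOL scores will fall below 0. That needs 1–5 coding, which the SAP does not give; its tables imply 1–5 for Physical Function and the emotional scales but 0–4 for the GI domains.

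Finally, belly pain counts "each belly pain area marked" yes in question 17, so prorating all items alike might seem to break that scale. This rests on inferred item ranges. If the other five items run 0–4, question 17 can reach 29 − 20 = 9. With question 17 answered and one other item missing, only the maximum sum overflows: 25 × 6/5 = 30, while 24 × 6/5 = 28.8 rounds up to 29. It merits at most a note.

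**Conclusion.** The point holds in limited form. The IBSQOL rule lacks a prorating step. Taken literally with 34-item limits it understates partly completed forms by 8.8 points (1–5 coding) or 5.9 points (0–4 coding) for a mid-scale respondent with 30 answers, and by more with fewer. Complete forms are unaffected.

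The nausea rule needs one stated domain size. Counted as three, it is wrong for complete forms with a non-zero score; counted as four, it is wrong for non-zero two-answer forms. The exactly-half gap also reaches Physical Function and the other GI domains.

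The affected results are exploratory outcomes reported in Table 33, in a study that stopped at 31 enrolled subjects and whose analyses SAP 14.2 expects to be mainly descriptive. With so few subjects a handful of forms can shift a group mean, but nothing in the documents shows that the errors would differ by arm. The primary and secondary endpoints are unaffected.

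**What to change.** In SAP 3.3:

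1. State the IBSQOL item coding. When 17 to 33 items are answered, replace the sum by the mean of the answered items times 34, or equivalently use the lowest score and range of the answered items.
2. For nausea, set raw = sum × 4/answered, rounded up, for every form with at least two of the three questions answered, at every visit, before using the 0–16 table.
3. For Physical Function and the GI domains, let prorating apply when 50% or less of the items are missing, so that it matches the threshold for giving a score.
4. Optionally, note that a prorated belly-pain raw score above 29 has no T-score.

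The cost is a few sentences and a small change to the scoring program, made before Table 33 is produced. No new data are needed.

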3.3. Study Definitions and Derived Variables

Diarrhea:

Diarrhea will be defined as Type 6 or 7 on the Bristol Stool chart.

Baseline Value:

The baseline value will be defined as the last value obtained prior to the first dose of study product unless otherwise noted.

Additional Nitazoxanide:

Any nitazoxanide reported as a concomitant medication will be considered additional nitazoxanide.

Initial Clinical Resolution of Norovirus Symptoms:

Clinical resolution of Norovirus symptoms will be assessed from the daily diary by the subject and will be defined as:

- Cessation of vomiting and,
- No stools classified by the Bristol Stool Chart as diarrhea (Type 6 or 7).

Subjects will need to have at least two consecutive daily diary entries where they reported no vomiting, no Bristol Stool Type 6, and no Bristol Stool Type 7 to meet the criteria for initial clinical resolution. There are several variables in the daily diary that indicate whether the subject had diarrhea or vomiting for that day.

Daily Diary Diarrhea Questions:

- Phase 1 (Treatment Phase):
 - Number of Bristol Type 6 stools? (Quantitative)
 - Were there too many Bristol Type 6 stools to count? (Qualitative)
 - Number of Bristol Type 7 stools? (Quantitative)
 - Were there too many Bristol Type 7 stools to count? (Qualitative)
- Phase 2 (Longitudinal Phase):
 - Did you have diarrhea today? (By diarrhea, we mean at least ONE bowel movement that could be described as Type 6 or 7.) (Qualitative)

Daily Diary Vomiting Questions:

- Phase 1 (Treatment Phase):
 - Did you have to take another dose because you threw up the first dose within 1 hour? (Qualitative)
 - How many times did you vomit today? (Quantitative)
- Phase 2 (Longitudinal Phase):
 - Did you vomit today? (Qualitative)

For a day to count towards clinical resolution during the treatment phase, the following responses must be recorded in the daily diary entry:

- Both quantitative diarrhea questions must be 0

- Both qualitative diarrhea questions must be missing (i.e. not “yes”)
- The quantitative vomiting questions must be 0
- The qualitative vomiting question must be “no”

For a day to count towards clinical resolution during the longitudinal phase, the following responses must be recorded in the daily diary entry:

- The qualitative diarrhea question must be “no”
- The quantitative vomiting question must be 0

If a daily diary entry is missing, refer to the imputation rules in Section [6.5](#).

Viral Load:

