Number of Type 6 or 7 Stools:

The number of Type 6 or 7 stools through Day 28 will be defined as the sum of the responses to the quantitative Daily Diary Diarrhea Questions during the Treatment Phase (see above). Missing responses will be left as missing.

Number of Days of IV Hydration or Total Parenteral Nutrition (TPN) Therapy:

The number of days of IV hydration or TPN therapy will be defined as the number of days with a concomitant medication with any indication related to IV hydration or TPN therapy. A blinded review of the concomitant medication data will be performed by the Medical Monitor to identify medications that should be included in the analysis. Days prior to Day 1 will not be included in the calculation of the number of days. Medications that are ongoing after Day 28 will be censored at 28 days.

Co-pathogen Status:

Co-pathogen status will be determined by the BioFire stool pathogen screen on Days 1 and 180. Co-pathogen status will be determined on Days 7, 14, 21, 28, 60, 120, and with recurrent diarrhea if unformed stool is present on study day. Analyses will only include whether pathogens were detected or not and will not differentiate by co-pathogen type. The listing will include which co-pathogens were detected at each subject/visit ([Listing 18](#)).

Secretor Status:

Saliva is collected at screening to determine H type 1 secretor status (phenotyping), while a buccal swab is collected to perform FUT2 genotyping. Phenotype and genotype results will either be “secretor” or “non-secretor” for each subject.

Norovirus-Specific Immunoglobulins (Ig):

Results below the lower limit of detection (LLOD) will be imputed as $\frac{1}{2}$ the LLOD. Results above the upper limit of detection (ULOD) will be imputed as the ULOD.

Responders:

A subject is classified as a responder if he or she has a four-fold or greater increase in Norovirus-specific Ig titers compared to baseline (Day 1).

Study Day:

Study day will be reported as the number of days from randomization with the day of randomization reported as study day 1.

Days Post-Randomization:

Days post-randomization will be reported as the number of days since randomization; if an event began on the day of randomization, the days post-randomization is reported as 0.

Duration:

Duration will be reported as the difference between the start and end dates, inclusive of the day the event started.

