6.5. Missing Data

All attempts were made to collect all data per protocol. Imputations will only be performed for missing daily diary data as it relates to the primary endpoint. Missing daily diary data for the primary endpoint will be handled as follows:

- Data that are missing after a subject has reached clinical resolution will not affect the primary time to event analysis and therefore will be ignored
- Subjects who drop out, are lost to follow-up, withdraw consent, or otherwise stop completing daily diary entries before clinical resolution will be censored on the day of their last completed diary
- Subjects with a gap in outcome data prior to clinical resolution will be handled depending on their last completed diary entry and their next completed diary entry:
 - If the last completed diary entry and the next completed diary entry have the same outcome (i.e., they are still symptomatic on both days or they have no symptoms on both days), then the gap will be imputed with the same outcome
 - If this imputation results in the subject being defined as having clinical resolution during this gap, their time to resolution will be the median of the interval
 - If the last completed diary entry and the next completed diary entry have different outcomes (i.e., the last one is symptomatic and the next one is asymptomatic, or vice versa), then the gap will be imputed with the symptomatic outcome (no resolution).

[Table 3](#) provides summary statistics (n, mean, median, standard deviation, minimum, and maximum) of the number of imputed diary days per subject given the above imputation rules and the number of overall missing diary days per subject. The above method will be considered the primary imputation method for the primary endpoint. In addition, a sensitivity analysis on the primary endpoint will be conducted using worst case scenario for subjects who drop out, are lost to follow-up, withdraw consent, or otherwise stop completing

daily diary entries before clinical resolution. These subjects will be censored at 180 days (i.e., assuming resolution of symptoms occurred after Day 180). [Listing 9](#) provides subject-level details for the number of diaries missed by week.

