The protocol calls for two-sample t-tests to be used for the below outcome measures. However, due to early closure of the study, the number of subjects is too small to meet the normality assumptions of the t-test; therefore Wilcoxon-Mann-Whitney exact rank sum tests will be used to compare treatment to placebo through Day 28 and/or Day 180 in the mITT analysis population (Table 30) for the following outcome measures (defined in Section 3.3):

- Number of days of diarrhea through Days 28 and 180.
- Number of stools classified by the Bristol Stool Chart as type 6 or 7 bowel movements through Day 28.
- Number of days of IV hydration or total parenteral nutrition (TPN) therapy through Day 28.

The following patient-reported outcome measures will be assessed using ANCOVA adjusting for the baseline patient-reported measure:

- Change in patient-reported quality of life as measured by EuroQOL-5 (global) and IBSQOL (diarrhea specific) [adult] or Euro QOL-5 Peds (global) and PedsQL GI Module [children] from baseline to Day 180.
- Change in patient-reported physical function as measured by the NIH PROMIS Physical Function (Adult) Pediatric Global Health (Peds) from baseline to Day 180.
- Change in patient-reported emotional distress as measured by the NIH PROMIS Depression, Anxiety, Fatigue (Adult and Peds) from baseline to Day 180.
- Change in patient-reported gastrointestinal symptoms as measured by the NIH PROMIS GI (Adult and Peds) symptoms (6 of 8 subscales) from baseline to Day 180.

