16.2.6 Individual Efficacy and Immunogenicity Response Data

Listing 12: 16.2.6.1: Individual Treatment Phase Daily Diary Data

[Implementation Note: “Too many” will be listed if number of stools was too many to count. If data is missing, it will be denoted as “—”. Rows will not be included for missing diary days. Imputation rules will not be included in the listings. Listing should be sorted by Treatment Group, Subject ID, Planned Time Point.]

Treatment Group	Subject ID	Transplant Type	Duration of Symptoms	Actual Study Day	Number of Bristol Type 6 Stools	Number of Bristol Type 7 Stools	Repeat Dose due to Vomiting	Number of Episodes of Vomiting
					[e.g. 7, Too Many]	[e.g. 7, Too Many]	Yes/No	

Listing 13: 16.2.6.2: Individual Longitudinal Phase Daily Diary Data

[Implementation Note: If data is missing, it will be denoted as “—”. Rows will not be included for missing diary days. Imputation rules will not be included in the listings. Listing should be sorted by Treatment Group, Subject ID, Planned Time Point.]

Treatment Group	Subject ID	Transplant Type	Duration of Symptoms	Actual Study Day	Diarrhea (At Least 1 Type 6 or 7 Bowel Movement)	Vomiting
					Yes/No	Yes/No

Listing 14: 16.2.6.3: Weekly Recall Diary

[Implementation Note: If data is missing, it will be denoted as “—”. Rows will not be included for missing weeks.]

Treatment Group	Subject ID	Transplant Type	Duration of Symptoms	Week Number ^a	Actual Study Day	Average Number Bowel Movements/Day	Average Number Vomiting Episodes/Day	% Type 6 or 7 Stool	% Type 3, 4, or 5 Stool	Abdominal Pain ^b	Urgency to Have Bowel Movement ^b	Fecal Incontinence ^b	Nausea ^b

^a Week Number is based off of Planned Time Point.

^b Subjects rated these symptoms as 0 being none and 10 being the worst possible.

Listing 15: 16.2.6.3: Individual PROMIS Scores Data – Quality of Life/PANAS

[Implementation Note: Listing will provide the PROMIS T-scores for IBSQOL. EurQOL Measures will be reported as ‘Problems’ or ‘No Problems’. Positive Affect and Negative Affect will be the reported scores based off of the Definitions in Section 3.3.]

Treatment Group	Subject ID	Transplant Type	Duration of Symptoms	Planned Time Point	Actual Study Day	Quality of Life (IBSQOL)	EuroQOL-5 Mobility	EuroQOL-5 Self-Care	EuroQOL-5 Usual Activities	EuroQOL-5 Pain/Discomfort	EuroQOL-5 Anxiety/Depression	EuroQOL-5 Health State	Positive Affect	Negative Affect	EuroQOL-5 Mobility

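### Diarrhea days and stool counts are raw diary totals, so unrecorded days score as symptom-free and, for stools only, uncountable days add nothing

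*SAP*

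**What the plan says.** SAP 3.3 counts a day towards days of diarrhea if "a quantitative diarrhea question must be greater than 0 or a qualitative question must be marked" yes. The number of Type 6 or 7 stools through Day 28 is "the sum of the responses to the quantitative Daily Diary Diarrhea Questions during the Treatment Phase". For both, the rule for gaps is "Missing responses will be left as missing". SAP 6.5 closes the other route: "Imputations will only be performed for missing daily diary data as it relates to the primary endpoint".

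Neither total has a denominator, a minimum diary completeness, proration or a dropout rule. SAP 8.3 sends both to testing: "Wilcoxon-Mann-Whitney exact rank sum tests will be used to compare treatment to placebo through Day 28 and/or Day 180", in the mITT population. The diary-compliance rule of the per-protocol population (SAP 6.3.2) therefore does not screen them.

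In the treatment-phase diary, whether there were too many stools to count is a yes/no item, separate from the numeric item, for each of Types 6 and 7 (SAP 3.3). In the Listing 12 shell, the words Too many stand in the stool-number column: they "will be listed if number of stools was too many to count". No numeric value is assigned to such an entry.

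**The concern.** A total over recorded days mixes how ill the subject was with how many diaries the subject returned. A subject with daily diarrhea whose last diary is Day 20 scores 20. That ranks better than a subject with complete diaries who resolves on Day 60. If one arm keeps poorer diaries or loses more subjects, its totals fall for that reason alone, and Table 30 prints a p-value for the difference.

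The stool count has a second fault. Only numbers are summed, so a day too bad to count can contribute zero.

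The SAP deals with similar gaps elsewhere. Several patient-reported scores are prorated with a 50% completeness rule (SAP 3.3), and the primary endpoint has gap rules and a worst-case dropout analysis (SAP 6.5). Protocol 8.1 says the weekly recall diary can offset missing daily data, but the SAP only lists those data (Listing 14) and does not use them in these totals.

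**Working it through.** The documents give no figure for these outcomes, so there is none to reproduce. The check applies the rules to single subjects and then to two arms with no true difference.

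**Inputs from the documents.** Placebo median 135 days and 20% attrition overall (SAP 5); 31 subjects enrolled (SAP 6.6). **Assumed.** A 16/15 split, exponential duration with diarrhea every day until resolution, all arm-specific dropout and missed-diary rates, and all stool rates.

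**1. One subject, diarrhea on all 180 days.** Complete diaries score 180. With 80% of diaries, 0.80 × 180 = 144. With the last diary on Day 30, the score is 30.

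**2. Stool sum to Day 28.** Assume 6 stools on ordinary days, 12 on uncountable days, and k uncountable days with no number. The recorded sum is 6 × (28 − k) and the true sum is 6 × (28 − k) + 12k.

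| k | Recorded | True |
|---|---|---|
| 0 | 168 | 168 |
| 5 | 138 | 198 |
| 10 | 108 | 228 |
| 14 | 84 | 252 |

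The most severe subject gets the best score. In days of diarrhea, each of these days still counts as one.

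**3. Expected arm difference under the null, Day 180.**
- Mean duration in the window: (135 / ln 2) × (1 − 2^(−180/135)) = 194.8 × 0.603 = 117.5 days.
- Missed diaries 25% against 5%, no dropout: −(0.25 − 0.05) × 117.5 = −23.5 days.
- Exponential dropout reaching a fraction q by Day 180 adds −ln(1 − q)/180 to the daily resolution rate of ln 2/135 = 0.00513. For q = 0.30 the total rate is 0.00712 and the mean is (1 − 0.70 × 0.397)/0.00712 = 101.5 days. For q = 0.10 it is (1 − 0.90 × 0.397)/0.00572 = 112.4 days. The difference is −10.9 days.

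**4. Rejection at 5%, 16 against 15, no true effect.** With one kind of missingness at a time, equal rates gave 4.5%, dropout 30% against 10% gave 6.5%, and missed diaries 25% against 5% gave 27%.

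A separate set of 2,000 runs had both kinds present and uniform dropout times. It used the Mann-Whitney test at software default, not forced exact.

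| Dropout | Missed diaries | Mean difference, days | Rejection |
|---|---|---|---|
| 20% v 20% | 10% v 10% | −0.3 | 4.6% |
| 30% v 10% | 10% v 10% | −9.1 | 6.7% |
| 40% v 10% | 10% v 10% | −13.6 | 9.5% |
| 20% v 20% | 25% v 5% | −21.3 | 20.5% |
| 40% v 10% | 25% v 5% | −33.8 | 37% |

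The missed-diary figure is lower here (20.5% against 27%) because 20% dropout in both arms adds spread and shortens observation.

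**5. Through Day 28.** Dropout of the same 30% against 10% by Day 180 gives 25.5 against 26.0 days and 4.5% rejection, so dropout hardly matters. Missed diaries still do: the mean in the window is 194.8 × (1 − 2^(−28/135)) = 26.1 days, and 20 percentage points of it is 5.2 days. The stool count was not simulated.

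**6. Same data, proportion of completed diary days with diarrhea.** Rejection was 4.5% to 5.5% in the one-kind-at-a-time runs. For missed diaries in the second set, the difference went from −21.3 to 0.0 days and rejection from 20.5% to 5.5%. For dropout 30% against 10%, the sign reversed: −9.1 became +5.3 days on a 180-day scale, or 5.3/180 = +0.03.

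**7. Poisson with log completed days as offset.** With full follow-up the variance of a subject's total is 2 × 194.8² × (1 − 0.397 × 1.924) − 117.5², about 4,130. That is about 35 times the mean. The z statistic is inflated by √35 = 5.9, so the false-rejection rate is P(|Z| > 1.96/5.9), about 74%. Simulation at 16 against 15 gave 71% to 74%.

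**The case against.** The strongest reply has four parts.

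- **The gap rule is ambiguous.** Leaving responses missing could mean that the subject's whole total is missing, which would drop incomplete diarists instead of crediting them. The SAP does not say, and the Table 30 shell has no row for the number analysed. This stands as a caveat. A sum over recorded days is the natural reading, and the other reading would need its own rule.
- **Uncountable days may carry a number.** The diary form is not in the documents. Listing 12 makes a missing number plausible but does not prove it. This also stands.
- **The harm needs unequal missingness.** A reader might infer that missing diaries by themselves create a false benefit. They do not: with equal rates the arm difference is about zero and the test keeps its level. The unequal rates above are assumptions, since the plan gives only 20% attrition overall.
- **The stakes are low.** These outcomes are exploratory, SAP 14.2 calls the updated analyses primarily descriptive, and Table 3 and Listings 9 and 12 would show an imbalance. That is fair, but showing an imbalance does not correct the p-value in Table 30.

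A reader might also infer that uncountable days drop out of days of diarrhea. SAP 3.3 rules that out, because a yes on the qualitative item is enough for the day to count. The primary endpoint is not affected either: it has its own imputation rules, and an uncountable day cannot count towards resolution.

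**Conclusion.** The point holds in a limited form. Both outcomes are unadjusted totals, so on the natural reading unrecorded days score as symptom-free for the individual subject. Between arms this becomes bias only when diary completion or dropout differs. At the enrolled size and under the assumed rates, the effect is large for unequal missed diaries (about −23 days, 27% rejection) and small for unequal dropout (about −11 days, 6.5%). It is absent when rates are equal. A larger inflation can be calculated for the planned 64 per arm, but that trial was not run.

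The uncountable-day fault is confined to the stool count and rests on such entries having no number. There it can reverse the ranking of subjects. Because the outcomes are exploratory, this should be corrected before treatment codes are opened, but it does not threaten the primary analysis.

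**What to change.** 1. Apply the planned exact Wilcoxon test to the proportion of completed diary days with diarrhea (through Days 28 and 180) and to Type 6 or 7 stools per completed diary day through Day 28. Add the number analysed and the completed diary days per arm to Table 30. State in SAP 3.3 how a subject with incomplete diaries is handled.
2. For an uncountable entry without a number, assign the larger of the subject's highest recorded daily count and a high percentile of the pooled, blinded counts. The subject's own maximum is not enough: in the k = 14 example it gives 84 + 14 × 6 = 168, a tie with the subject who had no such days.
3. Add a dropout sensitivity analysis, because the proportion slightly penalises early leavers. The Day 20 leaver now scores 20/20 = 100%. One option is to bracket the result by counting the days after the last diary first as all diarrhea and then as none.
4. Do not use an ordinary Poisson model with an offset, although Protocol 11.4.5 names a Poisson distribution as an option. Its false-rejection rate for Day 180 days is above 70%.

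The cost is SAP wording, changes to one table shell and a little extra programming. The daily diary data are already collected, and missing days are already summarised in Table 3 and Listing 9. Some bias remains if dropout is unequal.
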